#### **8.4. Subgroup Analyses**

For the 24-Week analysis, the change from baseline at Week 24 in Hgb, TSAT, ferritin, and phosphorus will be assessed for subjects who received 'Permitted' ESA therapy during the Dose Titration Period. For the Final analysis, the change from baseline at Week 24 and at Week 48 in Hgb, TSAT, ferritin, and phosphorus will be assessed for subjects who received 'Permitted' ESA therapy during the study.

Data in the Full Analysis Set for this subgroup of subjects will be used for the analyses. If at least 30 subjects are in the subgroup descriptive statistics and the two-sided 95% confidence intervals for the mean change from Baseline will be obtained as described in section 8.2 for the change from Baseline Hgb. If this subgroup includes at least 3 subjects but less than 30 subjects, only descriptive statistics will be presented for each of the starting dose treatment groups. For the Final analysis only, if less than 3 subjects are in the subgroup by subject listings of disposition, demographics, and laboratory tests (hematology, chemistry, urine chemistry, and miscellaneous) will be provided instead of summary tables.

It is expected that after the planned dose titration at Week 12 there will be about 35 subjects in each of the 4 dosing sequence groups,

(Starting Dose Group Daily Dose (pills/day) – Week 12 Titrated Daily Dose (pills/day), i.e.:

- 3 pills/day – 3 pills/day,
- 3 pills/day – 6 pills/day,

- 4 pills/day – 4 pills/day and
- 4 pills/day – 6 pills/day.

For the Final analysis, additional subgroup analyses will be conducted for change from baseline in Hgb, TSAT, ferritin, and phosphorus in these dosing sequence groups. The 95% confidence interval for the mean change from baseline for each dosing sequence will be obtained by using dosing sequence rather than starting dose treatment group in the MMRM model described in section 8.2. Each subject's dosing sequence group will be based on the actual dose prescribed at baseline and the Week 12 dose titration assignment. If the subgroups include at least 3 subjects but less than 30 subjects, the MMRM analysis will not be performed and only descriptive statistics will be presented. For the Final analysis only, if there are less than 3 subjects in any subgroup, only by subject listings will be provided instead of tables.

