9.2.1. Prohibited Therapy

Administration of any of the following therapies to subjects enrolled in the study starting with the Screening visit is not permitted:

1. IV iron
2. Blood transfusion
3. ESA with exception specified in Section 9.2.2
4. Oral iron therapy other than KRX-0502 as treatment for iron deficiency (multivitamins containing iron are permitted)
5. Phosphate binder other than KRX-0502
6. Commercial ferric citrate
7. Aluminum-containing therapies
8. Investigational drug other than the KRX-0502

If a subject receives a dose of IV iron or a blood transfusion (items 1 and 2 listed above), the subject will immediately discontinue study drug, complete the ET Visit assessments, and exit the study.

If a subject is to receive or has received any prohibited medication listed under items 3 to 8 above, the subject should be discussed with the Medical Monitor as soon as possible to determine the most appropriate course of action.

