9.2.2. ESA Rescue Therapy

ESA use is not permitted during the study. The exception is a scenario in which all of the following conditions for ESA rescue therapy are met:

1. A subject has had 2 consecutive Hgb values of <8.0 g/dL more than 3 days apart.
2. The Investigator decides to treat the subject with ESA as per standard of care.
3. The Investigator deems it appropriate for the subject to continue in the study.
4. The subject continues in the study on study drug.

Any subject who is to receive or has received ESA therapy regardless of whether its use constitutes permitted ESA rescue therapy or not should be discussed with the Medical Monitor as soon as possible to decide whether the subject may remain in the study.

Subjects who received ESA during the study and who remain in the study will be excluded from the PP analysis set. Subgroup analyses will be conducted for these subjects.

Subjects who have had 2 consecutive Hgb values of <8.0 g/dL more than 3 days apart but do not meet the other criteria of ESA rescue therapy should complete the ET visit and discontinue from the study.

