15.7. Efficacy Analyses

All efficacy analyses will be performed based on both the FAS and the PP analysis sets. The PP analyses will be considered primary and the FAS analyses will be considered as sensitivity analyses to assess the impact of subject exclusions.

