### 6.3.5. Per Protocol Analysis Set

The Per Protocol (PP) Analysis Set will include all subjects in the FAS who have no major protocol deviations that affect the validity of the efficacy measurements (see section 7.2) and have not received additional treatment that affect the validity of the efficacy measurements.

The following criteria exclude a subject from the PP Analysis Set:

- Receive red blood cell transfusions within 4 weeks prior to screening or at any time during the study.
- Receive ESAs (permitted or non-permitted) within 4 weeks prior to screening or at any time during the study.
- Receive IV Iron within 4 weeks prior to screening or at any time during the study.
- Pregnancy during screening or at any time during the study.
- Overall drug compliance < 50% i.e., from randomization to the Week 48 Visit date or to Early Termination date (whichever is earlier). (See section 7.4.1 Compliance Calculation)
- Major violations of eligibility criteria as determined by review prior to database lock.

The PP analysis set will be used for the 24-Week and Final analyses.

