**Table 3: Analysis Method and Analysis Set for Special Focus Efficacy Endpoints**

Efficacy Parameter	24-Week Analysis (Study Period: Dose Titration Period)	Final Analysis (Study Period: Entire Study)	Analysis Method	Analysis Set
Hgb	Change from Baseline to Week 24*	Change from Baseline to Week 48	MMRM	PP 
Hgb	Change from Baseline at Week 24	Change from Baseline at Week 48	ANCOVA	PP  Completers
Hgb	Time from Randomization to First Increase from Baseline Hgb >= 0.5 g/dL	Not Applicable	Kaplan-Meier	PP 
TSAT, ferritin, phosphate, bicarbonate, eGFR	Change from Baseline to Week 24	Change from Baseline to Week 48	MMRM	PP 
PTH, c-terminal and intact FGF-23	Change from Baseline to Week 24	Change from Baseline to Week 48	ANCOVA	PP 
FACIT score	Change from baseline at Week 24	Change from Baseline to Week 48	Descriptive	PP 
WPAI	Change from Baseline to Week 24	Change from Baseline to Week 48	Descriptive	PP 
Hospitalizations	Number and Duration ( days)	Number and Duration ( days)	Descriptive	PP 

Hgb, TSAT, ferritin, phosphate	Change from Baseline to Week 24	Change from Baseline to Week 48  Change from Baseline to Week 24	MMRM	FAS subjects who received permitted ESA Rescue Therapy
Hgb, TSAT, ferritin, phosphate		Change from Baseline to Week 48  Change from Baseline to Week 24	MMRM	PP Dosing sequence groups

\* Hgb change from baseline to Week 24 is the primary endpoint.

The analysis set used will either be the modified PP Analysis Set (24-Week Analysis snapshot) or PP Analysis Set (24-Week and Final Analysis).

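### The SAP limits the protocol's ESA subgroup analyses to permitted users without declaring the change, so a non-permitted ESA user who stays in the study is in no efficacy analysis

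*SAP*

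**What the plan says.** **Protocol.** Section 9.2.2 sets four conditions for permitted ESA rescue. It then addresses any ESA recipient, whose case, "regardless of whether its use constitutes permitted ESA rescue therapy or not should be discussed with the Medical Monitor", so that it can be decided whether the subject stays. The next paragraph has two sentences: "Subjects who received ESA during the study and who remain in the study will be excluded from the PP analysis set", followed by "Subgroup analyses will be conducted for these subjects". Section 9.2.1 makes IV iron or a transfusion a reason for immediate exit. For the other prohibited therapies, including ESA outside the rescue conditions, it says "the subject should be discussed with the Medical Monitor as soon as possible to determine the most appropriate course of action". Section 15.7 adds: "All efficacy analyses will be performed based on both the FAS and the PP analysis sets", with PP primary and FAS as sensitivity.

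**SAP.** Section 6.3.5 excludes from PP subjects who "Receive ESAs (permitted or non-permitted) within 4 weeks prior to screening or at any time during the study", and 6.3.6 repeats this for the modified PP set (mPP). The ESA efficacy subgroup is restricted throughout. Section 7.3 (baseline tables) and 8.1 tie it to rescue given under the protocol's conditions, Table 3 describes it as "FAS subjects who received permitted ESA Rescue Therapy", and 8.4 uses the same limit for the 24-Week and Final analyses; for the Final analysis, the changes from baseline "will be assessed for subjects who received 'Permitted' ESA therapy during the study". Section 9.6 withdraws the general FAS efficacy analyses and says the FAS is kept for the permitted rescue subgroup.

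**The concern.** The two protocol sentences refer to the same people: those excluded from PP for ESA use are those promised a subgroup analysis. The SAP reads the first sentence broadly (any ESA) and the second narrowly (permitted ESA). Some subjects therefore meet the exclusion but not the analysis that was meant to accompany it.

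Two things are at stake. The first is fidelity: a protocol-specified analysis is cut back, and the section that exists to list departures from the protocol does not say so. The second is completeness: with the FAS analyses withdrawn, the ESA subgroup is the only efficacy output left for subjects removed from PP for ESA use. If it covers only one kind of ESA user, the report cannot show how all ESA-treated subjects who continued on study drug fared.

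**Working it through.** The check is a trace of analysis sets. The documents give no planned ESA count to reproduce.

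**Step 1. Can a non-permitted ESA user remain in the study?** Yes. Protocol 9.2.1 and 9.2.2 leave it to discussion with the Medical Monitor. Protocol 9.2.2 does send out subjects with two consecutive Hgb values below 8.0 g/dL more than 3 days apart who fail the other rescue conditions. The retained non-permitted users are therefore mainly those given ESA without two such values.

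**Step 2. Where does this subject appear among the SAP efficacy analyses?**
- Primary and secondary MMRM (8.2, 8.3, Table 3): PP or mPP. Not included.
- ANCOVA at Weeks 24 and 48 for Hgb, iPTH and FGF23 (8.3): PP or mPP. Not included.
- Kaplan-Meier for first Hgb rise of at least 0.5 g/dL (8.3): PP or mPP. Not included.
- FACIT, WPAI and hospitalizations (Table 3): PP or mPP. Not included.
- Dosing-sequence MMRM (8.4, Table 3): PP. Not included.
- Box plots (8.3): no set is named, but 8.1 places efficacy analyses on PP/mPP. Not included on that reading.
- ESA subgroup (8.1, 8.4, Table 3): permitted only. Not included.
- General FAS efficacy analyses (Protocol 15.7): withdrawn in SAP 9.6.

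The number of efficacy analyses containing this subject is 0.

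**Step 3. What else would show this subject?**
- SAP 9.4 summarises laboratory values and changes for the whole Safety Analysis Set. Shift tables and by-subject listings cover Hgb, TSAT, ferritin and phosphorus.
- SAP 7.1 lists disposition with analysis-set flags.
- SAP 7.2 lists deviations for subjects excluded from PP, where non-permitted ESA use should appear.
- SAP 7.1.1 counts only those who left the study because of prohibited therapy, not those who stayed.
- SAP 7.5 cancels concomitant-medication tables and listings.
- The asterisk in listings (6.2, item 11) marks permitted users only.

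**Step 4. How many subjects?** The plan's sample-size figures reproduce: 1.96 × 0.9 / √140 = 0.149 g/dL, and 140 / (1 − 0.30) = 200. The point does not depend on them, but they give some scale. The planned loss to dropout and all PP exclusions together is 0.30 × 200 = 60 subjects, and retained ESA users are an unstated part of that. For the ESA subgroup to reach the 30 subjects at which 8.4 gives model-based confidence intervals, 30 / 60 = 50% of that allowance would have to be ESA recipients who stayed. At 3 to 29 subjects, 8.4 gives descriptive statistics only. Below 3, the Final analysis gives listings.

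**Step 5. Would widening the subgroup alter the reporting format?** With p permitted and q retained non-permitted users, the format differs only if p < 3 ≤ p + q or p < 30 ≤ p + q. The documents give neither p nor q.

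**The case against.** The strongest reply has four parts.

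- **The restriction is in plain view.** SAP 7.3, 8.1, 8.4 and Table 3 all state it, and 9.6 names the permitted subgroup. That is so. But 9.6 says only which analysis set this subgroup uses. It never says that the protocol's subgroup was wider, and a reader of 9.6 alone would not learn that it was reduced.
- **Protocol 9.2.2 is headed as rescue therapy, so its subgroup sentence may have meant rescue users only.** The preceding paragraph expressly covers both kinds of use, and the SAP itself reads the exclusion sentence as covering both. The two adjoining sentences cannot take different scopes without explanation.
- **The subjects are not lost to the report.** This stands. Someone might infer that they go unreported. Their laboratory data remain in the Safety Analysis Set outputs, and the deviation listing probably identifies them. None of those outputs is the promised subgroup analysis.
- **The consequence is small.** This largely stands. The subgroup is secondary, the study estimates changes and does not test a hypothesis, and the result is probably descriptive.

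It is also tempting to conclude that the omission hides treatment failures. Protocol 8.3.1 does cross-refer to 9.2.2 under lack of efficacy. However, the retained non-permitted users are mainly those without two confirmed low Hgb values, and the documents do not show why such a subject would have been given ESA.

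**Conclusion.** The SAP departs from Protocol 9.2.2 and does not declare it. A non-permitted ESA user who stays in the study is in none of the planned efficacy analyses, where the protocol would have included the subject in the ESA subgroup and in the FAS sensitivity analyses. This rests on reading the protocol's two sentences as having one subject, which their wording supports.

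The importance is modest. The number affected is unknown and could be zero. Nothing in the documents supports a claim that non-permitted users would outnumber permitted ones, or that including them would move the subgroup across a reporting limit. A reader might also infer that the primary result is distorted by this narrowing. It is not: the protocol itself removes ESA users from PP and makes PP primary, and correcting the subgroup returns nobody to that set. The loss of the FAS analyses is a separate change, which 9.6 declares.

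**What to change.** In SAP 7.3, 8.1, 8.4 and Table 3:
- Define the ESA subgroup as all FAS subjects who received any ESA during the study and remained in it, matching Protocol 9.2.2.
- Add a permitted/non-permitted flag. State which protocol version's Hgb threshold the flag uses, since SAP 7.1 and 7.1.2 carry both.
- Apply the existing 3-subject and 30-subject rules to the whole subgroup, and show the permitted subset within it.
- Report the count of each type by starting-dose group.

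If the narrower subgroup is intended, declare and justify it in SAP 9.6 as a change from Protocol 9.2.2, and list the other ESA users.

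The cost is wording and one derived flag on ESA data that the PP exclusion already requires. The wider subgroup is somewhat more heterogeneous, which the flag handles. Patient care, data collection and the primary PP estimate do not change.

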## 9. SAFETY AND TOLERABILITY

Safety and tolerability evaluation will be included in the 24-Week Analysis and the Final Analysis.

The safety data includes adverse events, vital signs and clinical laboratory measurements.

Adverse events that begin after the first administration of study medication or pre-existing conditions that worsen after the first dose of study medication are considered TEAEs. If, based upon the data recorded in the eCRF and/or the procedure for imputing the start date given in section 9.2.2, it is not possible to classify an AE as treatment emergent or not, then classify the AE as a TEAE.

For the 24-Week Analysis, since any table, listing or figure produced will only include statistics based upon the Screening period and Dose Titration treatment period:

- No adverse event that starts or worsens after the Week 24 visit date will be included in summaries of TEAEs and
- In calculating the subject months of study drug exposure only those days of treatment prior to the Week 24 visit will be counted since subjects are to delay taking their study drug on the day of planned site visits until after the site visit.

For the Final Analysis, all observations up to and including those for the Week 48 visit date will be included in identifying TEAEs and calculating subject months of study drug exposure.

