13.2.2. Recording Adverse Events/Serious Adverse Events

All AEs/SAEs will be collected for all randomized subjects from the date informed consent was signed to completion of the study or to the last administration of study drug or the Investigator/subject decision to discontinue treatment, whichever occurs later. Subjects will be followed for a 28-day follow-up period that begins with completion of the study or after the last administration of study drug, or after the Investigator/subject decision to discontinue treatment, whichever occurs later.

An SAE that occurs during the 28-day follow-up period must be collected regardless of relationship to study drug.

Any SAE reported to the Investigator following completion of the 28-day follow-up period must be promptly reported to the study's Sponsor if it is considered "related" by the Investigator.

The AE term should be reported in standard medical terminology when possible. For each AE, the Investigator will evaluate and report the following:

- Seriousness
- Relationship to study drug
- Action taken with the study drug
- Onset date
- Ongoing or resolution date
- Outcome
- Intensity (if applicable)

For all AEs, the Investigator must pursue and obtain information adequate to determine the outcome of the AE and to assess whether it meets the criteria for classification as an SAE ([Section 13.2.1.2](#)) requiring immediate action.

Changes in laboratory values, blood pressure, and pulse need not be reported as AEs. However abnormal values that are deemed clinically significant, lead to discontinuation of administration of study drug, or constitute an SAE must be reported and recorded as an AE.

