## 5.2. Final Analysis

The final analysis will be based on the full set of cleaned data for all visits up to and including the Week 48 visit (i.e. it will cover the Dose Titration Period and the Dose Maintenance Period).

Data for this analysis are the data for those subjects who completed the Week 48 visit or had Early Termination from the study prior to Week 48.

Some tables, listings and figures produced for the final analysis will display statistics for both the Dose Titration and the Dose Maintenance treatment periods.

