#### **9.2.3. Summaries of Serious Adverse Events (SAE), Adverse Event Dropouts, and Death**

For the 24-Week Analysis and the Final Analysis the number and percentage of subjects with serious treatment emergent AEs reported will be summarized by MedDRA system organ class and preferred term within each starting dose group and all treated subjects without regard to intensity or relationship to study drug. The SOCs will appear in descending order of number of subjects in the two treatment groups combined, i.e., all treated subjects, with at least one SAE mapped to the SOC. The PTs within each SOC will appear in descending order of number of subjects in the two treatment groups combined with at least one SAE mapped to the PT within that SOC.

The same types of tables as described for SAEs will be produced for:

- TEAEs leading to treatment discontinuation and
- TEAEs leading to deaths

A by subject adverse events listing will be produced to support these three tables. The list for the 24-Week Analysis will show all AEs for subjects who had at least one SAE or had treatment discontinued due to a TEAE or had a TEAE that led to death during the Dose Titration Period by starting dose group and subject number with the subject's AEs listed in chronological order of AE start date. Similarly, the list for the Final Analysis will be produced to show the AEs for subjects who experienced the same types of AEs either in the Dose Titration or Dose Maintenance period.

A listing of all adverse events of each deceased subject will be produced.

---

Document: \\quintiles.net\enterprise\apps\sasdata\sasb\sas\Keryx\KRX-0502\Biostatistics\Documentation\SAP\

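### Serious AEs starting in the 28-day follow-up are collected but fall outside the SAP's Week 48 cut-off for TEAEs, and early terminators have no stated cut-off

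*SAP*

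**What the plan says.** **Collection.** Protocol 13.2.2: "Subjects will be followed for a 28-day follow-up period that begins with completion of the study or after the last administration of study drug". A decision to stop treatment is a third possible starting point, and the latest of the three applies. The section adds: "An SAE that occurs during the 28-day follow-up period must be collected regardless of relationship to study drug". Collection of other AEs ends where this follow-up begins.

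**Definition.** SAP 9 defines TEAEs by a lower bound only: "Adverse events that begin after the first administration of study medication", together with existing conditions that worsen after the first dose. Protocol 15.8.3 is the same in this respect.

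**Cut-off.** SAP 9 then says of the Final Analysis that "all observations up to and including those for the Week 48 visit date will be included in identifying TEAEs". SAP 5.2 bases that analysis on the "full set of cleaned data for all visits up to and including the Week 48 visit" and takes its subjects as "those subjects who completed the Week 48 visit or had Early Termination from the study prior to Week 48".

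**Outputs tied to TEAE status.** SAP 9.1 has a row for serious TEAEs. In SAP 9.2.3, "the number and percentage of subjects with serious treatment emergent AEs reported will be summarized by MedDRA system organ class and preferred term", and tables of the same type are planned for TEAEs leading to death. The supporting listing for the Final Analysis covers events in the Dose Titration and Dose Maintenance periods.

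**Outputs not tied to TEAE status by their wording.** These are the separate SAP 9.1 rows for SAEs and for subjects who died, the serious-AE table in 9.2.1 item 5, the full AE listing in 9.2, and the 9.2.3 listing of all AEs of deceased subjects.

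**The concern.** The protocol obliges sites to collect serious events in a period that the SAP's rule for identifying TEAEs does not reach. A programmer who follows SAP 9 as written would leave those events unflagged, and the main serious-event and fatal-event tables by system organ class and preferred term depend on that flag. Long-term safety is part of the study objective, so a shortfall in these tables matters even if it is only a few events.

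Two further problems follow. The planned outputs use different bases (SAE, serious TEAE, death, TEAE leading to death), so their counts could differ with no explanation in the SAP. And a cut-off tied to the Week 48 visit date gives no date at all for a subject who never has that visit.

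**Working it through.** **1. The plan's own figures.** The only calculated figures in the documents are for efficacy precision. They supply the 140 and 200 used in step 5.
- Half-width: 1.96 × 0.9 / √140 = 0.149 g/dL, as stated in Protocol 15.2.
- Inflation for 30% loss: 140 / 0.70 = 200, as stated.

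The present point does not depend on either.

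**2. A completer's timeline.** The Week 48 visit has target Study Day 337 (SAP Table 2). If completion is the latest of the three starting points, the follow-up ends on Day 337 + 28 = Day 365. All of it lies after the Week 48 visit date.

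**3. An SAE in a completer with onset on Day 350, output by output.**

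| Output | Included? |
|---|---|
| SAP 9.1, serious TEAEs | No, if Week 48 is a cut-off |
| SAP 9.2.3, serious TEAEs | No, same reason |
| SAP 9.2.3, TEAEs leading to death (if fatal) | No, same reason |
| SAP 9.2.3, supporting listing | No, outside the two treatment periods |
| SAP 9.1, SAEs; subjects who died (if fatal) | Wording allows it; the 5.2 data scope leaves it unclear |
| SAP 9.2.1 item 5, serious AEs | Wording allows it, but it sits under a TEAE heading; same doubt from 5.2 |
| SAP 9.2, full AE listing | Yes by its wording |
| SAP 9.2.3, listing for deceased subjects (if fatal) | Yes by its wording |

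The 9.2.1 item 5 table and the 9.2.3 serious-TEAE table could therefore give different counts for the same terms.

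**4. An early terminator.** Take, as an example, a subject whose follow-up begins on Day 107. It ends on Day 107 + 28 = Day 135. An SAE on Day 120 meets the TEAE definition because it follows the first dose, and no Week 48 visit date exists to exclude it. If the programmer uses nominal Week 48, the event counts; if the Early Termination visit date is used instead, it does not. The completer's Day 350 event lies equally within follow-up and is left out.

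**5. Size.**
- Share of the window: 28 / (336 + 28) = 7.7% of 52 weeks, not counting screening.
- Subject-years of follow-up: 140 × 28 / 365.25 = 10.7, and 200 × 28 / 365.25 = 15.3.
- The documents give no SAE rate. I assume 0.2 to 0.5 per subject-year.
- Low end: 10.7 × 0.2 = 2.1 events. High end: 15.3 × 0.5 = 7.7 events.

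The plan's 140 is the number evaluable after dropout and per-protocol exclusion, not a count of completers. Some excluded subjects will complete, so 140 to 200 is a range for illustration.

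**The case against.** The strongest reply is that the Week 48 sentence includes and does not exclude. SAP 9 shows how an exclusion is written, for the 24-Week Analysis: "No adverse event that starts or worsens after the Week 24 visit date will be included in summaries of TEAEs". There is no matching sentence for Week 48, the TEAE definition is open-ended, and an AE that cannot be classified defaults to TEAE. So excluding follow-up events is not the only possible reading. It is still the natural one: the sentence names an end date, and SAP 5.2 ends the data there too. If no cut-off was intended, the sentence conflicts with the definition in the same section. Either way the text needs one clear rule.

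A second reply is that other outputs show these events, and this stands in part. A reader might infer that every SAE and death table omits follow-up events. The documents do not support that, because the 9.1 rows for SAEs and for subjects who died, 9.2.1 item 5 and two listings are not limited to TEAEs by their wording.

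A reader might also infer that any death in follow-up is lost. That does not hold either. The cut-off acts on onset or worsening, so a follow-up death from an event that began by Week 48 still counts as a TEAE leading to death, provided the outcome is in the database.

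Finally, the table shells are in a separate document that is not available here and may settle some of this.

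**Conclusion.** The point holds in a limited form. For completers, serious or fatal AEs that start or worsen after the Week 48 visit are left out of the 9.1 serious-TEAE row, the two 9.2.3 tables and their supporting listing, on the natural reading of SAP 9 and 5.2. Whether they reach the other SAE and death counts is unclear. SAP 9.6, which lists changes from the protocol's analyses, does not mention this narrowing of the protocol's open-ended TEAE definition.

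A reader might conclude that early terminators are under a different rule. The documents show only that no rule is stated for them; unequal treatment is a possible result, not a planned one.

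The 7.7% share follows from the visit schedule. The 2 to 8 events rest on an assumed SAE rate and an assumed number of completers, and should not be read as a count of events that will be missed. The 9.2.3 tables count subjects, so a follow-up event in a subject already counted under the same term adds nothing, and the effect on subject counts would be smaller. Sample size and efficacy analyses are unaffected. The change should be made because the stated cut-off undercounts serious events for which data will already exist.

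**What to change.** In SAP 9:
- State one upper bound for serious TEAEs and fatal TEAEs: from first dose to the end of the protocol's 28-day follow-up, for completers and early terminators alike.
- State the end date for non-serious AEs for both groups: the Week 48 or Early Termination visit, or the last dose if later, in line with how the protocol collects them.
- State that all SAEs and deaths collected through follow-up enter the 9.1, 9.2.1 item 5 and 9.2.3 tables.
- Separate this rule from the drug-exposure calculation, which shares the Week 48 sentence and should stay unchanged.

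Then extend the SAP 5.2 data scope and the 9.2.3 supporting listing to match.

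The cost is a few sentences and a small amount of programming; no new data are needed. The downside is that serious and non-serious AEs will have different windows, which should be footnoted on the tables.
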